### **Secondary Analyses of Primary Outcomes:**

These primary outcomes will also be assessed as time-to-event analyses (time-to-a-healed-wound and time-to-hernia-recurrence, respectively). In these analyses, the time-to-recurrence in the synthetic mesh group will be compared to

the time-to-recurrence in the biologic mesh group using a two-sided log-rank test. The null hypothesis is that the time-to-recurrence is the same between the two groups ( $H_0$ : Hazard Ratio = 1), and the alternative hypothesis is that the time-to-recurrence is significantly greater for the permanent synthetic mesh cohort compared to the biologic mesh cohort ( $H_1$ : Hazard Ratio  $\neq$  1). Since this is a randomized clinical trial, observed differences in other covariates between the two study groups are assumed to arise by chance. Therefore, the simple unadjusted analysis is sufficient to answer the research question, assuming adequate power (see above). However, since the association between other covariates and time-to-recurrence may be of interest and because group imbalances may occur due to chance, it is of interest to consider further analyses that adjust for covariates in the relationship of time-to-recurrence and mesh type. To that end, the following multivariable models are pre-specified: 1) Demographics: age, race, gender, and mesh type; and 2) Known linkages to hernia recurrence: BMI, history of smoking, size of defect, number of previous hernia repairs, and mesh type. These models will be fit with Cox proportional hazards models. If other covariates are found to be highly imbalanced between groups or found to be associated with time-to-recurrence, they can also be included in multivariable models; however, this type of post-hoc model selection is to be considered inferior to the pre-specified models and is speculative in nature. A similar analysis will ensue for the time-to-a-healed-wound outcome. The null hypothesis is that the time-to-a-healed-wound is the same between the two groups ( $H_0$ : Hazard Ratio = 1), and the alternative hypothesis is that the

time-to-a-healed-wound is significantly greater for the permanent synthetic mesh cohort compared to the biologic mesh cohort (H1: Hazard Ratio not= 1).

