We hypothesize that reinforcement of single-stage open repairs of complex abdominal wall defects with a macroporous light-weight polypropylene synthetic mesh will result in significantly lower rates of hernia recurrence (HR) and surgical site occurrences requiring procedural intervention (SSOPI) at 24 postoperative months, and greater cost-effectiveness compared to reinforcement with a biologic mesh. We further hypothesize that reinforcement with macroporous light-weight polypropylene synthetic mesh will be associated with a significantly greater change in preoperative to postoperative patient-reported quality of life (QOL) compared to reinforcement with biologic mesh for clean-contaminated or contaminated ventral hernias.

The specific aims of the proposal are:

1. To demonstrate that a single-stage repair of clean-contaminated (Class 2) or contaminated (Class 3) ventral hernias using a macroporous light-weight polypropylene synthetic mesh will result in superior clinical outcomes compared to a biologic mesh.
  - a. Task 1- Demonstrate that repairs of clean-contaminated and contaminated ventral hernias performed with macroporous light-

weight polypropylene mesh will result in fewer recurrent hernias and fewer surgical site occurrences requiring procedural intervention at 24 postoperative months compared to repairs of clean-contaminated and contaminated ventral hernias performed with biologic mesh.

- b. Task 2- Compare postoperative pain, and demonstrate greater change in preoperative to postoperative quality of life (QOL) at 1 month, 6 months, 12 months, and 24 months following clean-contaminated or contaminated ventral hernia repair with a macroporous light-weight polypropylene mesh versus a biologic prosthesis.

2. To demonstrate that a macroporous light-weight polypropylene mesh is the more cost-effective strategy than a biologic prosthetic in clean-contaminated and contaminated abdominal wall reconstruction.

- a. Task 1-Estimate direct and indirect economic costs associated with clean-contaminated or contaminated ventral hernia repair using either polypropylene mesh or biologic mesh from a limited societal perspective.
- b. Task 2 – Perform health utility valuation in patients undergoing repair of clean-contaminated or contaminated ventral hernias using either polypropylene mesh or biologic mesh.
- c. Task 3 – Calculate and compare incremental cost-effectiveness ratios for patients undergoing repair of clean-contaminated or

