CT scan as clinically indicated. Preoperative demographics and clinical data including sex, race, age, body mass index (BMI), location of the hernia, length and width of the hernia defect, wound classification(per CDC guidelines, table 1), smoking status (active within 3 month of surgery), medical history, surgical history of prior abdominal surgical procedures and prior ventral/incisional hernia repairs will be documented. Intraoperative details will include patient ASA score, patient temperature, use of epidural catheters, size of fascial defect (measured as maximal width and length), fascial layers released (external oblique, posterior rectus sheath, or transversus abdominis muscle), adhesions, concomitant procedures, wound characterization, mesh type, mesh placement, operative time, estimated blood loss, blood transfusion requirement, perioperative antibiotic administration (including type, dose, frequency, and times of initiation and discontinuation), and intraoperative fluid administration. Postoperatively, patients will be evaluated for signs and symptoms of complications along with presence or absence of surgical site infections (SSIs) per CDC definitions as categorized below (Appendix 4), presence or absence of surgical site occurrences (SSOs) and any procedural interventions required to treat these SSOs, presence or absence of hernia recurrence and any reoperations, length of hospital stay, discharge date, time to return of bowel function and any readmission. Wound erythema treated with antibiotics will be considered a wound cellulitis. Wounds that are opened and cultured will be appropriately categorized as postoperative SSIs based on CDC definitions. Type, dose, frequency, and duration of antibiotics will be recorded. Patients will also fill out HerQLes (Appendix 1) and

EQ-5D (Appendix 2) quality of life tools preoperatively and during each post-operative visit, at 4 weeks (± 2 weeks), 6 months (± 2 month), 12 months (± 3 months), and 24 months (± 4 months). See Appendix 7 for Plan for Continuation of Study Follow-up Visits for Patients Previously Enrolled at University Hospital. There is substantial evidence that the majority of hernia recurrences occur within the first 24 months after repair.[5, 15, 41]

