## **Surgical Site Occurrences Requiring Procedural Intervention**

A surgical site occurrence requiring procedural intervention (SSOPI) will be defined as a complication or adverse event occurring at a surgical site that is managed or treated with an invasive procedure. Consensus definitions and treatment plans for common SSOs following open complex ventral hernia repair were developed *a priori* by the co-investigators for the purposes of this study protocol (Appendix 6). All study co-investigators agree to follow these consensus definitions and treatment plans for study subjects enrolled in this trial to maximize objectivity of this study measure.

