### **Primary Analyses of Primary Outcomes:**

The primary outcomes are rates of surgical site occurrences requiring procedural intervention (SSOPI) and hernia recurrence (HR) assessed postoperatively at 1 month, 6 months, 12 months, and 24 months. For SSOPI with 4 repeated binary measurements, a generalized mixed model analysis with repeated measures will be performed to determine if a significant difference exists between the biologic mesh and the permanent synthetic mesh cohorts in the rate of SSOPI. For HR, which is a single binary outcome, simple chi-square tests will be used for unadjusted analyses and a logistic regression model will be used for adjusted analyses. As this is a randomized trial, differences in baseline demographic and clinical characteristics between the biologic mesh cohort and the permanent synthetic mesh cohort are expected to occur at random. Any significant differences found among the demographic or preoperative clinical characteristics between the two treatment groups will be controlled for in the final analysis to limit potential confounding of results.

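### The time-to-event version of the SSOPI co-primary outcome is time to a healed wound, a different and favourable event, with an alternative worded against the trial's aim

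*Combined protocol and SAP*

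**What the plan says.** *Primary Analyses of Primary Outcomes* names SSOPI first and hernia recurrence second. *Secondary Analyses of Primary Outcomes* then gives their time-to-event versions as "time-to-a-healed-wound and time-to-hernia-recurrence, respectively". The order pairs SSOPI with wound healing.

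The section on SSOPI defines it as "a complication or adverse event occurring at a surgical site that is managed or treated with an invasive procedure". *Study Design* frames the outcome as freedom from that event from surgery up to 24 months.

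For healing, the verbal alternative is that "time-to-a-healed-wound is significantly greater for the permanent synthetic mesh cohort compared to the biologic mesh cohort". The same sentence gives the formal alternative as a hazard ratio not equal to 1. The recurrence analysis uses a two-sided log-rank test, and a similar analysis is promised for healing. The recurrence alternative uses the same verbal form, with a greater time for synthetic mesh.

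*Specific Aims* sets out to show that repair with synthetic mesh "will result in superior clinical outcomes compared to a biologic mesh", including fewer SSOPI at 24 months.

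*Study Procedures* schedules visits "at 4 weeks (± 2 weeks), 6 months (± 2 month), 12 months (± 3 months), and 24 months (± 4 months". It lists surgical site occurrences and the procedures used to treat them among the data recorded. It lists no date of wound healing.

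**The concern.** The secondary analysis is presented as another assessment of a co-primary outcome, but it measures a different event. A patient who never has an SSOPI still has a healing time, and an SSOPI that arises after the wound has healed cannot appear in a time-to-healing curve. The two outcomes need not favour the same arm. *Anticipated results and limitations* expects that synthetic mesh may have more infections at first, which will settle with local measures and heal. That could mean slower healing without more SSOPI.

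The verbal hypothesis adds a second problem. A longer time to recurrence is good and a longer time to healing is bad, yet both are written the same way. A reader who takes the stated alternative as the hoped-for result would count slower healing with synthetic mesh as agreement with the hypothesis.

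Finally, the supplied text does not say what counts as a healed wound or where its date would come from.

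**Working it through.** **1. The plan's own figures.** The plan gives no sample size or power for time to a healed wound, so no stated figure is in dispute. The figures in *Power Calculation* reproduce:

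- Sample size: 202 / (1 − 0.20) = 252.5, rounded up to 253.
- Recurrence, 29.21% v 9.01%, 101 per arm, two-sided alpha 0.05 / 2 = 0.025 (z = 2.2414). The pooled proportion is 0.1911. The null standard error is √(2 × 0.1911 × 0.8089 / 101) = 0.0553. The alternative standard error is √[(0.2921 × 0.7079 + 0.0901 × 0.9099) / 101] = 0.0535. Then z = (0.2020 − 2.2414 × 0.0553) / 0.0535 = 1.46, so power is 92.8% (stated 92%).
- SSOPI, 39.02% v 9.01%, by the same formula as a single binary comparison: 99.8% (stated 100%, for four repeated measurements).

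None of these uses the healing analysis.

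**2. The event.** The two outcomes set side by side:

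| | SSOPI | Healed wound |
|---|---|---|
| Nature | adverse event | favourable event |
| Defined in the supplied text | yes | no |
| Patient with no surgical-site complication | has no event | still has a healing time |
| Complication after healing | counts | cannot appear |

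No rule in the supplied text converts one into the other.

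**3. The direction.** Under proportional hazards, a longer time with synthetic mesh means a hazard ratio (synthetic / biologic) below 1.

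| Event | Longer time with synthetic | Meaning |
|---|---|---|
| Recurrence | hazard ratio < 1 | benefit |
| First SSOPI | hazard ratio < 1 | benefit |
| Healed wound | hazard ratio < 1 | harm |

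The wording fits the aim for recurrence and would fit it for first SSOPI. It contradicts the aim only for healing.

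**4. The timing, if healing were dated only at visits.** The nominal visits fall at weeks 4, 26, 52 and 104, so the gaps are 4, 22, 26 and 52 weeks. With the windows, the first visit falls at weeks 2 to 6 and the second at months 4 to 8. At 52/12 weeks per month, months 4 to 8 are weeks 17.3 to 34.7. The interval between those visits therefore runs from 17.3 − 6 = 11.3 weeks to 34.7 − 2 = 32.7 weeks.

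The cost was gauged by simulation. The assumptions, none from the documents except the 101 per arm and the visit times, are exponential healing, a hazard ratio of 1.5, a two-sided log-rank test at 0.05, nominal visit dates and 300 runs per setting (Monte Carlo standard error about √(0.6 × 0.4 / 300) = 2.8 points).

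| Median healing, slower arm | Power, exact dates | Power, visit dates |
|---|---|---|
| 1 week | 77% | 37% |
| 1.5 to 8 weeks | 78 to 82% | 59 to 67% |

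In the 1-week case, 96% of patients are recorded as healed at the first visit. Visit-only dating is coarse and loses power but still carries information.

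**5. The replacement.** Suppose that 39.02% and 9.01% are 24-month cumulative risks of a first SSOPI and that hazards are proportional. The implied hazard ratio is ln(1 − 0.0901) / ln(1 − 0.3902) = −0.0944 / −0.4946 = 0.19. Expected events are 101 × (0.3902 + 0.0901) = 48.5. The Schoenfeld statistic is |ln 0.191| × √48.5 / 2 = 5.77. Subtracting 1.96 or 2.24 leaves power above 99.9% at two-sided 0.05 or 0.025. On the plan's own rates, the replacement is amply powered.

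**The case against.** The strongest reply is that little depends on this. The analysis is secondary. SSOPI has its own primary test, introduced with "For SSOPI with 4 repeated binary measurements", and a two-sided test gives the same p-value and hazard ratio whatever the sentence around it says. This stands, and it limits the severity.

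The slower-healing wording might also be deliberate, since an early excess of infections is expected with synthetic mesh. The plan does not say so. Even if it were deliberate, it would sit against the superiority aim without explanation.

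Appendix 5 (glossary) and Appendix 6 (definitions of surgical site occurrences) appear by title only, and the case report forms are not supplied. A definition of healing or a date field could be there. That would answer the question of where the date comes from. It would not turn healing into SSOPI or correct the direction.

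Two stronger readings are tempting. One is that the visit schedule makes healing impossible to time. The documents do not say that healing is dated only at visits, and even then the comparison keeps part of its power. The other is that the timing of SSOPI goes unexamined. It does not, because the primary model uses assessments at 1, 6, 12 and 24 months. What is missing is a time-to-first-event analysis.

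The lack of a listed date applies to the remedy as well. *Study Procedures* lists procedural interventions without expressly listing their dates, so the fix has to check this.

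**Conclusion.** The point holds as a should-fix. As written, a pre-specified secondary analysis of a co-primary outcome assesses a different event, and its verbal alternative describes a worse result for the arm that the trial aims to show is superior. The first conclusion rests on the plan's pairing of outcomes and its definition of SSOPI. The second rests on the plain meaning of a longer time to healing. Neither depends on the simulation. The timing weakness is conditional: it applies if scheduled visits are the only source of healing dates.

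A reader might infer that the trial's main result is compromised, or that the plan would report harm as success. The documents support neither. Sample size, power and the primary analyses do not use this endpoint. The formal alternative is non-directional, and nothing in the plan says that slower healing is to be read as benefit. I take the healing test to be two-sided because it is described as similar to the recurrence test and its formal alternative is two-sided.

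**What to change.** In *Secondary Analyses of Primary Outcomes*:

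- Replace time-to-a-healed-wound with time from surgery to first SSOPI, dated by the intervention procedure and censored at last contact or 24 months.
- Confirm that the case report form records the procedure date. If it does not, use the interval between visits and an interval-censored or grouped method.
- Test two-sided. State the expected direction as a longer time to first SSOPI with synthetic mesh (hazard ratio, synthetic versus biologic, below 1).
- If healing is kept, report it descriptively with a definition and a date source, and state that a shorter time is favourable.

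The cost is a change of wording in one section and one check of the case report form. No added patients or visits are needed. The formal comparison of healing times is given up. If procedure dates were not collected, the replacement also loses some precision in timing.

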### **Analyses of Secondary Outcomes:**

The secondary outcomes are pain and quality of life (QOL). The assessment of the association between these outcomes and mesh type will parallel what was described above for the primary outcome. The differences are as follows. First, the primary analysis will utilize an ANCOVA model adjusting for baseline pain (QOL) and correlations among repeated measurements. The null hypothesis is that the pain (QOL) is the same, on average, between the synthetic and biologic mesh groups (H0: Beta-mesh-type = 0). The alternative hypothesis is that the pain (QOL) is different, on average, between the two groups (H1: Beta-mesh-type not= 0). Second, the multivariable modeling will utilize multiple linear regressions. A mixed model analysis with repeated measures will be performed to determine if a significant difference exists between the biologic mesh and the permanent synthetic mesh cohorts in the mean change in score from the preoperative assessment to the postoperative assessments at 1 month, 6 months, 12 months, and 24 months for the EQ-5D and HerQLes quality of life instruments. The null hypothesis is that there is no significant difference between the biologic mesh and the permanent synthetic mesh cohorts in the mean change in score from the preoperative to the postoperative assessments at any of the time points for either the EQ-5D or the HerQLes quality of life instruments. The alternate hypothesis is that there is a significantly greater change in EQ-5D

and HerQLes scores from the preoperative assessment to the postoperative assessment at each of the time points for the permanent synthetic mesh cohort compared to the biologic mesh cohort

In these data analyses, we will explore the possibility of medical center effect and treatment by medical center interaction. In particular, in the regression analyses, we will use indicator variables for medical center effect and indicator variable\*treatment for possible treatment by medical center interaction. If treatment by medical center interaction is significant, then it is more appropriate that the treatment effects are summarized by medical center.

**Specific Aim 2 - Demonstrate that a macroporous light-weight polypropylene mesh is the more cost-effective strategy than a biologic prosthetic in clean-contaminated and contaminated abdominal wall reconstruction.**

The first task to address this specific aim will be to estimate direct and indirect economic costs associated with clean-contaminated and contaminated open ventral hernia repair. A micro-costing approach will be used assuming a limited societal perspective. Costs associated with the preoperative, operative, and postoperative phases of care will be considered as it pertains to the management of the ventral hernia. In most cases, one to two preoperative clinic visits will be necessary. Final operative costs will be based on each patient's actual inpatient encounter cost obtained from the participating institutions. Postoperative costs

will account for routine outpatient visits, costs incurred for complications, and time lost from work due to ventral hernia management. All costs will be reported in U.S. dollars, adjusted for the years in which the data were obtained. Should institutional data not be available for a particular cost, the best available evidence from currently published analyses will be used. The second task for this specific aim is to perform health utility valuation in patients undergoing open repairs of clean-contaminated and contaminated ventral hernias. Patients will be administered the EQ-5D and the HerQLes instruments at one preoperative visit and postoperatively at scheduled visits at 4 weeks ( $\pm 2$  weeks), 6 months ( $\pm 2$  month), and 12 months ( $\pm 3$  months), and 24 months ( $\pm 4$  months). HerQLes and EQ-5D valuations will be converted to health utility estimates based on published norms from the Agency for Healthcare Research and Quality (AHRQ). Quality-adjusted life years (QALYs) will be calculated based on these health utilities obtained in the postoperative phase. For a given strategy (light-weight macroporous polypropylene mesh or biologic mesh), it is anticipated that health utility variation will be affected more than survival. As such, calculations of QALYs will assume that all patients survive during the 24 month follow-up period, but differ in their health utility valuation.

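### The quality-of-life hypotheses are spread over two unreconciled models, and the one naming EQ-5D and HerQLes pairs an 'any visit' null with an 'each visit' alternative, so no decision rule is defined

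*Combined protocol and SAP*

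**What the plan says.** All of this is in the combined protocol and SAP, mostly under Analyses of Secondary Outcomes.

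- **First model.** For pain and quality of life, "the primary analysis will utilize an ANCOVA model adjusting for baseline pain (QOL) and correlations among repeated measurements". It has one two-sided null: "The null hypothesis is that the pain (QOL) is the same, on average, between the synthetic and biologic mesh groups", written as Beta-mesh-type = 0. No instrument is named.
- **Second model.** A repeated-measures mixed model then compares the arms "in the mean change in score from the preoperative assessment to the postoperative assessments at 1 month, 6 months, 12 months, and 24 months" for EQ-5D and HerQLes. Its covariates are not listed. Its null is no significant difference "at any of the time points for either the EQ-5D or the HerQLes quality of life instruments". Its alternative is a significantly greater change in both scores from the preoperative to "the postoperative assessment at each of the time points for the permanent synthetic mesh cohort".
- **The aim.** Aim 1 Task 2 under Specific Aims, repeated under Approach, is to "demonstrate greater change in preoperative to postoperative quality of life (QOL) at 1 month, 6 months, 12 months, and 24 months". That matches the wording of the second model.
- **Error rate.** The only alpha statement, under Power Calculation, is 0.05 two-sided overall for two hypotheses, which are the two primary outcomes. No alpha, testing order, decisive visit or decisive instrument is given for quality of life.

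**The concern.** Better quality of life with synthetic mesh is a named hypothesis of the trial. A reader who follows the label goes to the ANCOVA and its single average effect. A reader who follows the aim, or looks for the two instruments by name, goes to the change-score model. The plan does not say how the two relate or what is concluded if they disagree.

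The second model also lacks a usable rule of its own. Its null fails if there is a difference at one visit on one instrument; its alternative needs a difference in one direction at every visit on both. A result between the two contradicts the null without supporting the alternative. If the model omits baseline, it is also the less precise of the two and carries any chance baseline imbalance into the estimate.

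**Working it through.** **1. What the plan supplies.** It gives no SD, effect size, pre-post correlation or power for quality of life, so there is no stated figure on this point to reproduce. The nearest is the hernia recurrence power: 101 per arm, 29.21% against 9.01%, stated as 92%. The pooled normal formula gives 92.8% at two-sided 0.025 and 96.0% at 0.05. The stated power therefore fits 0.05 split between the two primary outcomes, with none of it assigned to quality of life. The sample size also reproduces: 202 / 0.8 = 252.5, rounded up to 253.

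**2. The gap between null and alternative.** Four visits times two instruments is 8 points. Let each point be synthetic better, no difference, or biologic better. That gives 3^8 = 6,561 patterns. The null is one of them (no difference at all 8) and the alternative is one (synthetic better at all 8). The other 6,559 belong to neither. This counts patterns; it is not a probability.

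**3. Reading A: any one of eight tests at two-sided 0.05 suffices.** Under independence the error is 1 − 0.95^8 = 0.337. For correlated tests it was simulated with 400,000 multivariate-normal draws, taking the correlation between two points as the visit correlation times the instrument correlation. All correlations are assumptions.

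| Visit correlation | Instrument correlation | Any of 8, either direction | Any of 8, favouring synthetic |
|---|---|---|---|
| 0.3 | 0.3 | 0.311–0.318 | 0.160–0.166 |
| 0.5 | 0.5 | 0.269–0.284 | 0.135–0.145 |
| 0.7 | 0.7 | 0.208–0.229 | 0.104–0.115 |

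The lower value in each cell has equal correlation between visits; the higher has autoregressive correlation.

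**4. Reading B: all eight must favour synthetic mesh.** In the same simulations the error is at most 0.0005. Power is the difficulty. Assume a benefit of 0.4 SD at every point, 101 per arm and a raw change score. Single-test power is 67% at a pre-post correlation r of 0.3 and 81% at r = 0.5. If the tests were independent, power for all eight would be 0.671^8 = 0.04 and 0.811^8 = 0.19. With correlations of 0.5–0.7 between the tests it is about 21–55%; the top of that range takes r = 0.5 and all eight statistics correlated 0.7 with one another.

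**5. Precision, only if baseline is omitted from the second model.** Take equal SDs (set to 1) before and after surgery. At a single visit the raw change has variance 2(1 − r) and the ANCOVA residual has variance 1 − r². Their ratio is (1 − r²) / [2(1 − r)] = (1 + r)/2.

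| r (assumed) | Change score | ANCOVA | Ratio | Power at 0.4 SD, change / ANCOVA |
|---|---|---|---|---|
| 0.2 | 1.60 | 0.96 | 0.60 | not computed |
| 0.3 | 1.40 | 0.91 | 0.65 | 67% / 85% |
| 0.5 | 1.00 | 0.75 | 0.75 | 81% / 91% |
| 0.7 | 0.60 | 0.51 | 0.85 | 96% / 98% |
| 0.8 | 0.40 | 0.36 | 0.90 | 99.4% / 99.7% |

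**6. If baseline is included.** Write change as Y − B = a + b·mesh + c·B. Then Y = a + b·mesh + (c + 1)·B, with the same b. The mesh effect equals the ANCOVA effect and no precision is lost.

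**7. After the fix.** One test per instrument at 0.05 each gives 1 − 0.95² = 0.0975 across two independent instruments. At 0.025 each, or in a fixed order at 0.05, the error is at most 0.05.

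**The case against.** The strongest reply is that the plan already has what is asked for: a primary analysis, adjusted for baseline, with a single null. That stands as far as the label goes. A reader might infer that the quality-of-life hypotheses are decided by the change-score model, and the documents do not support that. Aim 1 Task 2 names no model, and a baseline-adjusted ANCOVA also addresses change. What the label leaves open is why a second model, with different hypotheses, carries the only statement about EQ-5D and HerQLes.

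A reader might also infer that the plan runs at a 34% false-positive rate. It does not say that any one of eight tests wins. A mixed model can be tested globally, the written alternative is conjunctive and directional, and counting only results in favour of synthetic mesh brings the simulated range down to about 10–17%. The supportable statement is that the rule is undefined.

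Third, a loss of 25–40% in precision is not established. Omitting baseline is the natural reading, because the first model lists it and the second does not, but the text does not say so. The second model could even be describing how the ANCOVA is fitted. The plan also controls for preoperative characteristics that differ significantly between arms, and says the secondary analyses parallel the primary ones. At most that adjusts for baseline quality of life when a significance test happens to flag it.

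Finally, these are secondary outcomes. That is correct and limits the severity.

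**Conclusion.** The point holds as a gap in specification. Two models with different hypotheses address the same question, their roles are not reconciled, and the one tied to the named instruments pairs a null and an alternative that leave most results unassigned. The same data could be reported as supporting or not supporting Aim 1 Task 2.

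The numerical consequences are conditional. The error is 34% (independence) or about 21–32% (assumed correlations 0.3–0.7) if any of eight counts, and below 0.001 with low power if all eight are required. The ANCOVA variance is 0.60–0.75 of the change-score variance at r = 0.2–0.5 and 0.85–0.90 at r = 0.7–0.8, given equal SDs and baseline omitted; there is no loss if baseline is included. The documents give none of these correlations. The error rate for the two primary outcomes and N = 253 are not affected. The sponsor should correct this, but it does not threaten the trial's main conclusions.

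**What to change.** Make the baseline-adjusted model the only confirmatory quality-of-life analysis.

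- **Model.** Fit one repeated-measures mixed model per instrument, with the four postoperative scores as outcome and mesh, visit, mesh-by-visit, baseline score, center and wound class as covariates. Center and wound class are the randomization strata. The plan already explores center in its regressions, but does not name wound class for these models.
- **Test.** Test each instrument once, using the mesh difference averaged over the four visits as the meaning of Beta-mesh-type = 0. Write the contrast out: with a mesh-by-visit term and reference coding, the mesh coefficient alone is the effect at the reference visit.
- **Two instruments.** State a fixed order for EQ-5D and HerQLes, or test each at 0.025.
- **Visits.** Report visit-specific differences as estimates with confidence intervals.
- **Remove.** Replace the any/each hypotheses and the separate change-score model.

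The cost is SAP wording: same data, same visits, one model fewer. The small downside is that a difference at a single visit is no longer a stand-alone claim.
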